11 STATISTICAL CONSIDERATIONS

11.1 HYPOTHESES AND SAMPLE SIZE CALCULATION

11.1.1 SAMPLE SIZE FOR THE PRIMARY EFFECTIVENESS ENDPOINTS

First Primary Effectiveness Endpoint

The first primary effectiveness endpoint is the reduction in the unmedicated diurnal IOP from baseline to 12 months postoperatively. The study objective is to show that the mean unmedicated diurnal IOP reduction of the study treatment (i.e. ab-interno transluminal viscoelastic delivery and trabeculotomy performed with OMNI system performed after uneventful cataract extraction) is superior to that of the cataract extraction alone. Based on recent approved MIGS studies, the mean \pm SD unmedicated diurnal IOP reduction at 12 months for the cataract extraction alone is 6.7 mmHg \pm 3.6 mmHg (N = 118) for Glaukos P170043 and 6.3 mmHg \pm 4.0 mmHg (N = 187) for Ivantis P160024. Therefore, the mean \pm SD unmedicated diurnal IOP reduction at 12 months for the cataract extraction alone is estimated as 6.5 mmHg \pm 3.8 mmHg.

The corresponding statistical hypotheses are as follows:

$H_0: \mu_{OMNI} \leq 6.5$ mmHg and $H_a: \mu_{OMNI} > 6.5$ mmHg, where μ_{OMNI} is the mean unmedicated diurnal IOP reduction at 12 months for the OMNI Surgical System in combination with Cataract Extraction.

Based on a one-sample t-test with a one-sided significance level of 0.025 (or two-sided 0.05), a sample size of 116 eyes at 12 months provides a statistical power of 80% at a true μ_{OMNI} of 7.5 mmHg.

Second Primary Effectiveness Endpoint

The second primary effectiveness endpoint is the reduction in the number of IOP-lowering medications from screening to 12 months (before medications washed out if applicable) postoperatively.

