The study objective is to show that the mean reduction in number of IOP-lowering medications of the study treatment at 12 months is not inferior to that of the cataract extraction alone. Based on P170043 and P160024, the mean \pm SD of reduction in number of IOP-lowering medications at 12 months for the cataract surgery alone is 0.9 ± 0.8 and 1.1 ± 1.1 , respectively. Therefore, the mean \pm SD of reduction in the number of IOP-lowering medications at 12 months for the cataract surgery alone is estimated as 1.0 ± 1.0 . A non-inferiority margin of 0.25 is considered. Therefore, a difference between the mean reduction in number of IOP-lowering medications for the cataract alone (1.0) and the mean reduction in number of IOP-lowering medications for the study treatment (MOMNI), $1.0 - M_{OMNI}$, of < 0.25 indicates that the study treatment is not inferior to the cataract alone in reducing the number of IOP-lowering medications.

The corresponding statistical hypotheses are as follows:

$H_0: M_{OMNI} \leq 0.75$ and $H_a: M_{OMNI} > 0.75$ (i.e. $1.0 - M_{OMNI} < 0.25$).

Based on a one-sample t-test with a one-sided significance level of 0.025 (or two-sided 0.05), a sample size of 101 eyes at 12 months provides a statistical power of 80% at a true M_{OMNI} of 1.0 medication.

Sample Size for the Primary Effectiveness Endpoints

Both of the alternative hypotheses of the two primary effectiveness endpoints need to be achieved in order to prove the study treatment effect, so the significance level adjustment for the multiplicity is not performed for the primary effectiveness endpoints. Therefore, based on the two primary effectiveness endpoints discussed above, a sample size of 116 eyes at 12 months is needed. Considering a drop-out rate of about 10%, approximately 130 eyes should be enrolled and treated with the study treatment.

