11.4.1 PRIMARY EFFECTIVENESS ENDPOINTS

The IOP reduction from baseline to 12 months postoperatively and the reduction in number of IOP-lowering medications from baseline to 12 months will be calculated for each eye and summarized descriptively. The 95% confidence interval of the mean reduction will be derived based on the t-distribution. The one-sample t-test will be performed for testing the statistical hypotheses described in Section 11.1.1. It should be noted that, for eyes with secondary surgical interventions (SSI) to control IOP or with SSI that can affect the IOP before 12 months, the last available observed data before the SSI will be used to impute the 12-month data. For the analyses based on the mITT population, the following imputation for subjects with missing 12-month data but without SSI may be performed:

- The within-eye worst IOP (collected after 3 months postoperatively or IOP at baseline for the subjects with no data after postoperative 3 months) for the missing 12-month IOP and worst number of IOP lowering medications (collected after 3 months postoperatively or IOP-lowering medication data at baseline for the subjects with no data after postoperative 3 months) for the missing 12-month number of IOP-lowering medications.
- The worst IOP (collected after 3 months postoperatively or IOP at baseline for the subjects with no data after postoperative 3 months) during the study for the missing 12-month IOP and worst number of IOP-lowering medications (collected after 3 months postoperatively or IOP-lowering medication data at baseline for the subjects with no data after postoperative 3 months) during the study for the missing 12-month number of IOP-lowering medications.
- The mean IOP during the study for the missing 12-month IOP and mean number of IOP-lowering medications during the study for the missing 12-month number of IOP-lowering medications.
- The last-observed-carry-forward approach.

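### The mITT missing-data rules in 11.4.1 are optional, unranked and partly undefined, so near the planned effect the mITT IOP result depends on which rule is run

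*Combined protocol and SAP*

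**What the plan says.** Section 11.2 makes the per-protocol (PP) population primary. PP requires 12-month IOP and medication data, except in eyes with an SSI. A non-SSI eye with a missing outcome therefore leaves the primary analysis and returns only in the supportive mITT analysis.

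For those eyes, 11.4.1 says "the following imputation for subjects with missing 12-month data but without SSI may be performed" and gives four rules:

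1. Within-eye worst: "The within-eye worst IOP (collected after 3 months postoperatively or IOP at baseline for the subjects with no data after postoperative 3 months".
2. A second worst rule that omits the within-eye label. It keeps the baseline clause "for the subjects with no data after postoperative 3 months) during the study for the missing 12-month IOP".
3. The mean during the study.
4. LOCF.

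Parallel wording covers the drug count. No rule is named as the main one. Section 11.4.2 uses the same imputations to derive the secondary responses.

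Table 1 in Section 9.1 schedules one IOP visit between month 3 and month 12. It is at month 6 (Day 150-210) and is an ordinary Goldmann reading. The unmedicated diurnal IOP is taken only at baseline and at month 12, or at the month-12 washout visit.

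**The concern.** There are three difficulties.

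- **Rule 1 is seldom a worst case for an eye seen at month 6.** When one reading is available, the worst and the last are the same. If the eye was on drops at that visit, a medicated pressure stands in for an unmedicated one, which favours the treatment.
- **Rule 2 has no settled meaning.** Read within the eye, it repeats rule 1. It may also mean that every missing eye receives the highest value in the pool. Or it may mean the study's highest value for eyes with later data and own baseline for the rest. Two programmers could follow the text faithfully and get different answers.
- **Nothing says which rule counts.** Because imputation is optional, the mITT test could be run without any, or with whichever rule is preferred once results are known.

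At stake is whether the mITT analysis can tell a reader how far missing eyes would have to fall short before a co-primary conclusion is lost.

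**Working it through.** **Inputs from the plan (11.1.1).** The plan uses a "one-sample t-test with a one-sided significance level of 0.025 (or two-sided 0.05), a sample size of 116 eyes at 12 months" that "provides a statistical power of 80% at a true" reduction of 7.5 mmHg. The null is 6.5 and the SD 3.8. "Considering a drop-out rate of about 10%, approximately 130 eyes should be enrolled and treated with the study treatment".

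**Reproducing the plan's figure.** A noncentral-t calculation with difference 1.0, SD 3.8 and one-sided 0.025 gives N = 116 with power 80.3%. Then 116/0.9 = 128.9, so 129 against the stated 130. The plan therefore expects about 130 − 116 = 14 eyes without month-12 data. I take mITT as 130 eyes: Section 11.1.3 raises treatment to about 145 because some treated eyes, which mITT excludes, were on no medication at screening.

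**Fixed-value check.** Let 116 completers have mean c and SD 3.8, and give 14 missing eyes values vᵢ:

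- m = (116c + Σvᵢ)/130
- s² = [115 × 3.8² + 116(c − m)² + Σ(vᵢ − m)²]/129
- t = (m − 6.5)/(s/√130)

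Example with c = 7.5, seven eyes at 7.5 and seven at 0: m = 922.5/130 = 7.096; s² = (1660.6 + 18.9 + 1.1 + 352.5)/129 = 15.76, so s = 3.970; t = 0.596/0.348 = 1.71; one-sided p = 0.045.

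| Case at c = 7.5 | Mean | p | At 0.025 |
|---|---|---|---|
| Completers only | 7.50 | 0.003 | pass |
| Rule 1, all 14 seen at month 6 and like completers | 7.50 | 0.001 | pass |
| Rule 1, 7 seen and 7 lost early | 7.10 | 0.045 | fail |
| Rule 1, all 14 lost early (reduction 0) | 6.69 | 0.31 | fail |
| Rule 2, 7 eyes at −5 and 7 at own baseline | 6.42 | 0.57 | fail |
| Rule 2, all 14 at −5 | 6.15 | 0.77 | fail |
| Rule 2, all 14 at −11 | 5.51 | 0.95 | fail |

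The −5 and −11 assume that the study's highest IOP lies 5 or 11 mmHg above the eye's own baseline. The documents give no such figure.

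**Tipping point.** Setting all 14 eyes to one value, the test is lost once that value falls to about 4.2 mmHg when completers average 7.5, about −2.2 at 8.5, and about −10.7 at 10.

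**Ordering under the third reading of rule 2.** Take an eye with baseline 24 and month-6 IOP 14. If the study's highest value is 30, it scores 24 − 30 = −6. An eye lost before month 6 scores 0. This reversal occurs whenever the study's highest value exceeds the eye's own baseline.

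**Simulations (4,000 runs each).** Rule 2 is taken in its third reading. The pass rates at a true 7.5 mmHg are:

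| Scenario | LOCF | Rule 1 | Rule 2 |
|---|---|---|---|
| A: 13 missing at random, 8 seen at month 6; baseline centred on 25 within 21-36, month-6 noise SD 2.5 | 84% | 51% | 0.4% |
| A with 6 missing | 84% | 74% | 17% |
| B: 14 missing, 7 lost early; baseline 24.5, SD 3, within 21-36, month 6 to month 12 correlation 0.6 | 86% | 38% | 0% |
| B with none lost early | 85% | 85% | 0% |

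In B with 7 lost early, at a true 8.5 the rates are 100%, 100% and 47%; at a true 10 all are 100%. In B the study's highest IOP came out at about 28-30 mmHg, and the reversal affected 83-95% of eyes with month-6 data.

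**The case against.** Several stronger conclusions are tempting, and the documents do not support them.

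- **That rule 1 never has more than the month-6 reading.** Section 9.9 provides for unscheduled visits. An eye on medication at month 12 that misses only the washout visit has a month-12 reading, though a medicated one. The month-3 window runs to Day 98, so a few of those visits may also count.
- **That rule 2 penalises well-followed eyes.** This holds under only one of three readings. Within the eye there is no such effect. If every missing eye gets the pool maximum, the order is not reversed either.
- **That neither worst rule is severe.** Read across eyes, rule 2 is very harsh: −5 or −11 mmHg lies far below the 4.2 mmHg tipping point. The fault is incoherence, not leniency.
- **That the simulated loss under rule 1 comes from relying on one reading.** It does not. In scenario A the mean of 7.21 equals 7.5 × 125/130, that is, five early losses set to zero. The eyes seen at month 6 cost nothing. Varying the number seen from 5 to 13 of 13 moves the pass rate from 29% to 85%, which reflects only the assumed drop-out timing.

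The LOCF figures also assume that early-lost eyes carry forward values averaging the full month-12 effect. The simulations treat month 6 as a noisy version of the month-12 unmedicated value. Rule 3 and the medication co-primary were not simulated.

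Finally, PP is primary, the plan attaches no success criterion to mITT, and sensitivity analyses are expected to differ. All of this stands. It limits the point without removing it: the rules remain optional, unranked and, for rule 2, undefined.

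**Conclusion.** The point holds in a limited form. For most non-SSI eyes that miss month 12, rule 1 and LOCF give the same month-6 value, which may be medicated. Rule 2 cannot be programmed without a decision that the text does not make. At or near the planned effect with about 10% missing, the mITT IOP test runs from a likely pass to a near-certain fail according to the rule chosen and, under rule 1, according to when eyes are lost.

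The spread depends on assumed baseline values, noise, drop-out timing and highest study IOP. It narrows as the effect grows. At a true 10 mmHg all simulated rules pass. The exception in the fixed-value check is extreme: all 14 eyes at −11 gives p = 0.030.

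A reader might infer that the trial's success turns on this choice. It does not, because the formal tests are primary in PP. What is lost is a usable answer from the only planned analysis that brings back the eyes PP drops.

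**What to change.** In 11.4.1, replace the optional list with one required mITT analysis:

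- Multiply impute the missing 12-month unmedicated diurnal IOP and drug count. Use baseline IOP, screening drug count and all available post-operative IOP and drug data, including month 6 with drug status at that visit.
- Apply a stepped penalty to the imputed values (for example 1 mmHg, or 0.25 drug), to zero reduction and beyond if needed. Report the penalty at which each co-primary is lost.
- Derive the 11.4.2 responses from the same imputed data.
- Keep the other rules only as secondary sensitivity analyses. Delete rule 2, or define it so that eyes lost early are scored no better than eyes seen later.

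The cost is SAP wording, some programming, and a short table in place of a single figure. No new data are needed.

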9.9 MANAGEMENT OF IOP AFTER SURGERY

This protocol recommends that no IOP-lowering medications should be administered to subjects after the surgery (0 meds on postop day 1) unless medically warranted. Investigators should use their clinical judgement in determining when and why IOP-lowering medications should be reintroduced and if a subject requires surgical re-intervention to manage IOP.

Re-introduction of hypotensive medications should follow the guidelines below:

- The same medication class(es) as used preoperatively should be re-introduced. Dependent on preoperative IOP medication use, the reintroduction/addition of IOP medications postoperatively should follow the order below:
 1. Prostaglandin Analogues
 2. Alpha Agonists
 3. Beta Blockers
 4. Rho Kinase Inhibitor
 5. Carbonic Anhydrase Inhibitors (CAIs)
- No more than one ocular hypotensive agent should be added at a single visit or within a 2-week period.

³² 180° trabeculotomy should be attempted in every eye enrolled in the study. There is a possibility that 180° trabeculotomy may not be possible in each case.

In the event of a steroid response (IOP increase), the usual guidelines requiring a reproducible increase in IOP should be followed; however, topical hypotensive medications should be discontinued once the topical steroid has been discontinued.

If a pressure rise is observed, a paracentesis may be performed as necessary. If a paracentesis is performed and there is no protocol-defined adverse event, the paracentesis will be documented in the subject's medical record, the applicable visit CRF and the Ocular Procedures log. If, however, the paracentesis is performed in conjunction with an AE, then the AE is recorded as such, and the paracentesis is also recorded on the AE CRF as a treatment for the protocol-defined AE (as well as the other CRFs mentioned above).

Medications which have been re-started by the investigator may be discontinued if the investigator's judgment is that the target intraocular pressure has been reached and the continued use of some or all of the therapy may not be required. Discontinuation of medications after re-introduction is recommended to be in the reverse order of re-introduction. The rationale for discontinuation will also be documented on the follow-up form by the investigator.

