11.2 ANALYSIS POPULATIONS

The intent-to-treat (ITT) analysis population includes all subjects who are enrolled and treated, regardless of whether or not they have a protocol deviation. Due to the eligibility revision in May of 2019 on requiring at least one ocular hypotensive medication, the modified ITT (mITT) population includes all ITT except for the treated eyes that were not on any ocular hypotensive medication at the screening visit. The per-protocol analysis population (PP) is a subset of mITT, which includes all subjects who have taken at least one ocular hypotensive medication at screening and have uneventful cataract extraction followed by ab-interno transluminal viscoelastic delivery and trabeculotomy, 12 month IOP and medication data, and have no clinically significant protocol deviations. It should be noted that the mITT subjects with an uneventful study procedure but with SSIs before the 12-month visit will be included in the PP population even if they do not have the 12-month IOP and medication data. The primary analyses on the primary and secondary endpoint analyses will be carried out on the per-protocol population.

The safety data will be summarized based on the ITT population. The primary and secondary endpoint analyses will also be performed on the mITT population.

The data will be listed separately for the enrolled subjects that are not treated with OMNI and treated subjects that do not have ocular hypotensive medications at the screening.

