11.4.2 SECONDARY EFFECTIVENESS ENDPOINT

The number and percent of eyes achieving the secondary effectiveness endpoint will be calculated. The binomial distribution will be used to derive the exact 95% confidence interval of the percent and to perform the statistical hypotheses for the secondary effectiveness endpoint described in Section 11.1.2. It should be noted that, for eyes with secondary surgical interventions (SSI) to control IOP or with SSI that can affect the

IOP before 12 months, the non-responder (i.e. do not achieve the secondary effectiveness endpoint) will be assumed for the missing 12-month response.

For the analyses based on the mITT population, the IOP and number of IOP-lowering medications imputation for missing data described in Section 11.4.1 will be used to derive the corresponding response of the secondary effectiveness endpoint.

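### Two of the four optional mITT imputation rules (study mean and LOCF) have no after-3-months limit, so early drop-free visits can lower the imputed 12-month medication count and favour the treatment

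*Combined protocol and SAP*

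**What the plan says.** Section 11.2 makes per-protocol the main analysis: "The primary analyses on the primary and secondary endpoint analyses will be carried out on the per-protocol population". That population requires 12-month data, except in eyes with a secondary surgical intervention (SSI). The mITT analysis is therefore the one that has to deal with dropout.

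For mITT, Section 11.4.1 says "the following imputation for subjects with missing 12-month data but without SSI may be performed" and gives four options:

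1. Within-eye worst value, restricted to data "collected after 3 months postoperatively or IOP at baseline for the subjects with no data after postoperative 3 months".
2. Worst value during the study, with the same restriction.
3. "The mean IOP during the study for the missing 12-month IOP and mean number of IOP-lowering medications during the study", with no visit window. The text does not say whether the mean is within eye or across eyes, or whether screening and baseline count.
4. "The last-observed-carry-forward approach", also with no window.

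The interval carries no stated allowance for imputation: "The 95% confidence interval of the mean reduction will be derived based on the t-distribution". Under Section 11.4.2 the same filled-in values decide mITT responder status: "imputation for missing data described in Section 11.4.1 will be used to derive the corresponding response".

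Table 1 schedules IOP and a medication log at Day 1, Week 1 and Months 1, 3 and 6. Section 9.9 recommends that "no IOP-lowering medications should be administered to subjects after the surgery (0 meds on postop day 1) unless medically warranted", and lets at most one agent be added per visit or two-week period.

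**The concern.** Medication counts are expected to start near zero after surgery and to rise in eyes that need drops again. A mean over all post-operative visits pulls such an eye's imputed 12-month count towards zero. LOCF does the same for an eye whose last visit was early. The plan guards against this in two rules and not in the other two.

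The second primary endpoint tests the mean medication reduction against a null of 0.75, a margin of only 0.25 below the assumed 1.0. A small favourable error in the imputed eyes uses up a visible part of that margin. No mITT rule is designated as the main one, so a favourable result could be given the emphasis. A separate question is whether filled-in values, treated as observed, make the t interval too narrow.

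**Working it through.** **Inputs from the plan.** Section 11.1.1: SD 3.8 mmHg for IOP reduction, true mean 7.5 against null 6.5, one-sided 0.025, 116 eyes at 12 months; medication SD 1.0, null 0.75, margin 0.25; dropout about 10%, approximately 130 treated. Section 5: mean medications at 6 months of 0.4 (5 combined-surgery eyes in one case series) and 1.1 (a 20-eye series, 13 with cataract surgery).

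**Assumptions.** The per-eye visit patterns, the IOP values, and Month 6 standing in for the true 12-month count.

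**The plan's own figure.** A one-sample t-test with difference 1.0, SD 3.8 and one-sided 0.025 has 80.25% power at n = 116. Then 116/0.90 = 128.9, so 129, stated as approximately 130. I use 116 observed and 14 missing eyes.

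**Medication count.** Shift in the mean reduction = (Month 6 count − mean of five visits) × 14/130.

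| Day 1, Wk 1, M1, M3, M6 | Mean | M6 | Shift | Share of 0.25 |
|---|---|---|---|---|
| 0,0,1,1,1 | 0.6 | 1 | 0.043 | 17% |
| 0,0,0,1,1 | 0.4 | 1 | 0.065 | 26% |
| 0,0,1,2,2 | 1.0 | 2 | 0.108 | 43% |
| 0,0,0,0,2 | 0.4 | 2 | 0.172 | 69% |
| 0,0,0,0,0 | 0 | 0 | 0 | 0% |
| 1,1,1,0,0 | 0.6 | 0 | −0.065 | conservative |

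Each row supposes that every missing eye follows that pattern. At exactly 10% missing, 0.4 × 0.10 = 0.04, which is 16% of the margin.

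**Ceiling.** The understatement cannot exceed the true count. If missing eyes average 0.4 medications, the shift is at most 0.4 × 0.10 = 0.04 (16%). At 1.1 it is at most 0.11 (44%).

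**Pre-operative visits included.** With a screening count of 2 and a washed-out baseline of 0, the pattern 0,0,0,1,1 averages 4/7 = 0.57, still below 1. An eye never restarted averages 2/7 = 0.29, slightly above its true 0.

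**Eye lost early.** An eye last seen at Week 1 with counts 0,0 is imputed 0 by both the mean rule (post-operative visits only) and LOCF. The worst-value rules send it back to baseline. The Baseline visit follows washout, however, so that fallback gives a real count only if it uses the screening value (1-4 under inclusion criterion 4).

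**Effect on the test.** I simulated 10,000 trials at the 0.75 null: SD 1.0, 14 of 130 eyes imputed by a within-eye mean of five visits, within-eye correlation 0.5, missing at random. An optimistic error of 0.4 per imputed eye raises one-sided error from 0.025 to about 0.067; an error of 1.0 raises it to about 0.21.

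**IOP.** Take 16 mmHg at Months 1, 3 and 6. Day 1/Week 1 values of 12/13 give (12+13+48)/5 = 14.6; values of 22/18 give 17.6; values of 28/20 give 19.2. The first looks better than 16 and the others worse. Adding screening 19 and baseline 25 gives 16.7, 18.9 and 20.0, all worse.

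**Interval width, across-eye mean.** With 13 of 130 missing (10%), the imputed eyes add nothing to the sum of squares but count in n. Estimated SE / correct SE = √(116/129) × √(117/130) = 0.948 × 0.949 = 0.90. The critical value 1.979 becomes 1.979 × 0.90 = 1.78 in effect, so one-sided error is about 3.9%. Simulation with 14 missing gives about 4% and 92% coverage.

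**Interval width, within-eye mean.** With unbiased imputed values, coverage stays at about 95%. Under this reading the harm is bias, not standard error.

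**The case against.** The strongest reply is that this is one of four optional sensitivity analyses, listed beside two deliberately harsh ones, and it cannot change the per-protocol result. That is correct and limits the weight of the point.

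Several stronger readings are tempting, and the documents do not support them:

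- A reader might infer that the plan prescribes averaging in Day 1 and Week 1. It permits this by silence; it does not state it. The same silence would admit screening and baseline. Section 9.9 names only Day 1 for zero drops and makes a recommendation with a medical exception.
- A reader might infer that missing eyes also look better on IOP. Few drops early means less medicated readings, and Section 5 reports IOP spikes at 1-2 days (5 cases in a 10-eye series), which would make eyes look worse.
- A reader might add the two harms together. The visit-pattern bias is worked for the within-eye reading; the too-small standard error needs the across-eye one.
- A reader might take the medication bias as certain for each eye. Section 9.9 also has drops stopped after a steroid response or once target pressure is reached, so a falling count such as 1,1,1,0,0 is imputed conservatively.

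It can also be said that the window changes little: read strictly, only Month 6 lies after 3 months and before 12, so a windowed mean, LOCF and the within-eye worst value would coincide apart from unscheduled visits. That holds for eyes seen at Month 6. It does not hold for eyes lost before then, where the mean rule and LOCF now use near-zero early counts. Nor does LOCF err when the last value is at Month 6 and the count is stable; its problem is confined to early losses.

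**Conclusion.** The point stands as a limited defect in the supportive mITT analysis, worth correcting. The missing window on the mean and LOCF rules can give a too-favourable medication result. The illustration of 0.4 medications per missing eye costs 16-17% of the margin at about 10% missing. Larger shifts need larger assumed counts in the missing eyes, and eyes that never restart drops contribute nothing unless pre-operative visits are averaged in. No per-eye pattern is a figure from the documents.

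For IOP no direction can be claimed. There is a mismatch of measure, though: under Table 1, unmedicated diurnal IOP is taken only at baseline and 12 months, and the visits between have ordinary readings that may be on drops. Filling an unmedicated endpoint from those readings is questionable under either rule.

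The narrow interval is a separate and conditional finding: SE about 10% too small and one-sided error about 3.9% at 10% missing, only if the mean is across eyes.

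**What to change.** Replace the mean rule with multiple imputation combined by Rubin's rules, using pre-operative and post-3-month IOP and medication data, and add a tipping-point shift showing how much worse the missing eyes must be to lose each primary conclusion. Name it as the main mITT method.

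At minimum:

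- apply the after-3-months window to the mean and LOCF rules, and say whether the Month 3 visit falls inside it;
- give both rules a pre-operative fallback, using the screening medication count because baseline is after washout;
- state that the mean is taken within eye.

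The cost is SAP wording, a little more programming, and possibly a slightly less favourable mITT estimate. No visit or measurement changes.
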